5.6 Discharge or 7 Days (whichever occurs first)

The following assessments will be performed per site routine practice at discharge or 7 Days post procedure:

- National Institutes of Health Stroke Scale (NIHSS)
- Modified Rankin Scale (mRS)
- Glasgow Coma Score (GCS) – (MIS only)
- SAE collection

5.7 90 Day Follow-Up ±14 Days (Optional phone visit)

The following assessment will be performed per site routine practice at this optional phone visit:

- Modified Rankin Scale (mRS)

Table 1: Schedule of Assessments

ACTIVITY	Baseline Evaluation	Procedure	Discharge or 7 Days ⁶	90 Day Follow-Up ¹ (±14 Days)
Informed Consent²	X			
Medical History	X			
Demographics	X			
Medication Review	X	X		
Clot Retrieval		X		
Blood Sample Collection		X		
Hematoma Volume³		X		
NIHSS	X		X	
mTICI⁴		X		
mRS	X ⁵		X	X
GCS³	X		X	
Serious Adverse Events⁷		X	X	

¹Optional Visit (conducted by phone)

² May be obtained up to 1 calendar day post-procedure and must be obtained prior to shipment of samples

³ Minimally invasive surgery / hematoma evacuation patients only

⁴ Ischemic stroke patients from digital subtracted angiography

⁵ Historical (pre-stroke)

⁶ Whichever occurs first

⁷ The following SAEs will be collected through 7 days post procedure: Device related events, procedural related events, Symptomatic ICH (sICH) at 24 hours, symptomatic embolization of new territory (ENT) at end of procedure

6. Specimen Collection and Shipment

All specimen should be placed within the provided collection tube(s) then securely packaged in the specimen collection kit provided, and shipped to the Core Lab(s) as quickly as possible, but no later than 72 hours post procedure and after informed consent is obtained.

The study sponsor will provide specimen kits, comprised of the following components:

- Mini Sample collection tube(s) for the clot
- Sealable plastic biohazard bags
- Absorbent material
- Paraffin tape for mini sample collection tubes(s)
- Purple collection tubes for blood samples (x2)
- Return packaging for specimen shipment to the Core Lab(s)
- UN 3373, Biological substances, Category B label
- Instructions for specimen collection, packing and shipping the specimen kit

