16.1 Modified Rankin Scale ²⁷

0	No symptoms
1	No significant disability, despite symptoms; able to perform all usual duties and activities
2	Slight disability; unable to perform all previous activities but able to look after own affairs without assistance
3	Moderate disability; requires some help, but able to walk without assistance
4	Moderately severe disability; unable to walk without assistance and unable to attend to own bodily needs without assistance
5	Severe disability; bedridden, incontinent, and requires constant nursing care and attention
6	Death

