2.2 Secondary Objectives

To prospectively collect and correlate data relating patient's clinical presentation, hospital course, and length of hospital stay to specimen histology, RNA sequencing, SNPs, and proteomic analysis.

3. Sample size

Due to the descriptive nature of this registry with no formal statistical hypothesis test, sample size calculations were not performed. Up to 400 subjects will be enrolled in the registry.

4. Interim analysis

No interim analyses are planned for the purpose of stopping the study early. Interim analysis may be performed for publication of registry results. No adjustments will be made to the confidence bounds for the final analysis.

5. General Statistical methods

No formal statistical testing is planned for this study. All statistical analyses will be descriptive in nature. Descriptive statistics will include the number of observations, mean, median, standard deviation, inter-quartile range, minimum and maximum for continuous variables and counts and percentages for discrete variables. All confidence intervals presented will be two-sided. Analyses will be conducted using SAS (SAS Institute, Cary, NC).

6. Patient Disposition

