7.1 Intent to treat

All enrolled subjects will be analyzed under the intent-to-treat (ITT) principle.

8. Statistical Analysis

This plan is limited to the analysis of clinical data and specimen histology. The number of patients enrolled, patients completing the study, patients not completing the study, and patients completing the optional 90 Day Follow-Up visit will be summarized. Clot characteristics, such as clot location, clot organization, composition, clot etiology, clot dimensions, and specimen histology, will be summarized using descriptive statistics¹. Baseline data including, but not limited to demographics, clinical, procedural, and imaging characteristics from ischemic stroke patients and patients eligible for minimally invasive hematoma evacuation will be summarized using descriptive statistics. Exploratory multivariate analyses will be conducted. Results collected at multiple

visits will be summarized at each visit for which they are collected as described in Schedule of Assessments Table. Summaries for all measures will include all observed data for each visit.

9. Analysis of adverse events

Serious adverse events will be collected in this registry on patients treated with any of the RED reperfusion catheters from procedure through discharge or 7 days post-procedure. Serious device related adverse events, serious procedure related adverse events will be summarized by showing the number and percent of subjects which report the event.

Other safety events collected on the case report form through 7 days post procedure will include symptomatic ICH at 24 hours, and symptomatic embolization of unininvolved or new territory (ENT)

All information pertaining to adverse events noted during the study will be listed by subject, detailing category, date of onset, date of resolution, relation to device or procedure and seriousness. The onset of serious adverse events will be shown relative (in number of days) to the day of procedure.

10. Subgroup analysis

To evaluate the impact of baseline conditions on procedural and clinical outcomes as well as clot characteristics, subgroup analyses will be performed for procedural outcomes of mTICI score, clinical outcomes of mortality at 90 days, NIHSS score at discharge and the proportion of patients that achieve mRS of 0 to 2 at 90 days (if available) and clot characteristics of gross appearance, clot sign, size, weight, volume and histology.

The subgroups below will be used for these analyses:

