- *Stroke type (Ischemic or Hemorrhagic)*
- *Location of Intracerebral Hemorrhage (Deep or Lobar)*
- *Age (Less than 65 or 65 and older)*
- *Gender (Male or Female)*

- *Race (White, Black, Asian or Any other)*
- *Ethnicity (Hispanic or Non-Hispanic)*
- *Smoking status (Current, Former or Never smoked)*
- *Covid status (Active, Previous or No History of COVID)*
- *Time of stroke onset to procedure. (6 or less hours or More than 6hrs in Ischemic subgroup only)*

Descriptive statistics and 95% confidence intervals will be presented for each subgroup and the difference between subgroups. Notable differences between subgroups will be further evaluated using additional covariates and multivariate modeling to describe relationships between subgroups and clinical outcomes. These analyses will be performed in the Intent-to-Treat population given adequate numbers for robust analysis.

11. Pooling across centers

Analyses will be presented using data pooled across centers. Descriptive statistics for key variables such as age, baseline NIHSS, IV rtPA administration, stroke type, target vessel location, mTICI, and mRS will be presented to assess any potential site effects. If there is evidence of site heterogeneity, additional analyses will be performed to determine confounding factors influencing site and clinical outcomes. Appropriate stratified and modeling techniques, including contingency tables, logistic regression, and random effects will be used to assess differences between study centers to justify pooling data across centers. To avoid the influence of small enrolling sites on contingency tables, low enrolling sites will be removed as a sensitivity test for contingency table analyses.

12. Lost to follow-up and missing data

Every effort will be made to keep all missing data to a minimum. Patient discontinuation rates will be tabulated by the reason for early termination. Any

loss of viable or insufficient sample will be noted. The primary analysis will be data as observed.

13. Central Core and Pathophysiology Lab

In addition to the analysis detailed above, up to three independent laboratories will follow the Study Core Lab Charter to analyze collected samples via histology, proteomics, transcriptomics, and genomics.

14. Changes to planned analysis

All changes to the statistical analysis plan (SAP) will be documented in a revised SAP or in the clinical trial report.

15. References

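### SAP section 10 compares the seven-level 90-day mRS between subgroups only at two separate binary cuts (0-2, and death), so shifts within 0-2 or within 3-5 go unseen and no estimate uses the full scale

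*Combined protocol and SAP*

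**What the plan says.** Protocol section 16.1 defines the mRS on seven levels, 0 to 6, with 6 being death. Level 4 is "Moderately severe disability; unable to walk without assistance and unable to attend to own bodily needs without assistance" and level 5 is "Severe disability; bedridden, incontinent, and requires constant nursing care and attention". The mRS is the only item listed for the 90-day contact in protocol section 5.7, which begins "The following assessment will be performed per site routine practice at this optional phone visit".

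SAP section 10 names the outcomes to be compared across subgroups. Two of them concern status at 90 days: "clinical outcomes of mortality at 90 days", and "the proportion of patients that achieve mRS of 0 to 2 at 90 days (if available". On output it says: "Descriptive statistics and 95% confidence intervals will be presented for each subgroup and the difference between subgroups". It plans no distribution, shift or ordinal comparison of the 90-day mRS by subgroup. Notable differences go on to multivariate modelling whose form is left open.

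Elsewhere the mRS is summarised by visit (SAP section 8) and by site (SAP section 11), but not by subgroup. On inference, SAP section 5 says "No formal statistical testing is planned for this study", and SAP section 3 says "sample size calculations were not performed".

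**The concern.** The registry collects an ordered score and compares it between subgroups as two yes/no outcomes. Two subgroups with the same 0-2 proportion and the same mortality look identical at 90 days, even if survivors in one mostly walk unaided (level 3) and in the other are mostly bedridden (level 5). A difference between full recovery and slight disability is lost in the same way.

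Precision is also at stake. Intervals for subgroup differences are the planned output. They come from at most 400 patients, across two diseases and nine subgroup factors, with a 90-day call that is optional. If the difference between subgroups runs along the whole scale, an estimate based on one cut is less precise than the collected data allow. The cut may also influence which differences count as notable and so go on to modelling.

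**Working it through.** The plan states no power, effect size or mRS distribution, so there is no figure of its own to reproduce. The check asks how much of the information in the seven-level score each planned comparison keeps.

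**Inputs from the documents.** Seven levels; cuts at 0-2 versus 3-6 and at 0-5 versus 6.

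**Assumptions, not in the documents.** Proportional odds, and three illustrative distributions over levels 0 to 6, in percent:
- A: 10, 17, 18, 15, 15, 7, 18 (0-2 proportion 45%, deaths 18%)
- B: 5, 10, 15, 18, 20, 10, 22 (30%, 22%)
- C: 1, 4, 10, 17, 25, 13, 30 (15%, 30%)

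**Formulas.** For a common log odds ratio, the information per patient is proportional to:
- full scale: (1 − Σp³)/3, where p are the seven level proportions;
- one binary cut with proportion g on one side: g(1 − g);
- three groups (0-2, 3-5, 6) in one ordinal model: (1 − Σq³)/3, where q are the three group proportions.

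Information kept is the ratio to the full scale. The relative interval width on the log-odds scale is 1/√(information kept).

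**Full scale.**
- A: (1 − 0.0247)/3 = 0.3251
- B: (1 − 0.0300)/3 = 0.3233
- C: (1 − 0.0508)/3 = 0.3164

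**0-2 cut alone.**
- A: 0.45 × 0.55 = 0.2475; 0.2475/0.3251 = 76%; interval 15% wider
- B: 0.30 × 0.70 = 0.2100; 0.2100/0.3233 = 65%; 24% wider
- C: 0.15 × 0.85 = 0.1275; 0.1275/0.3164 = 40%; 58% wider

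**Mortality alone.**
- A: 0.18 × 0.82 = 0.1476; 45%
- B: 0.22 × 0.78 = 0.1716; 53%
- C: 0.30 × 0.70 = 0.2100; 66%

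**Better of the two planned comparisons.** 76%, 65% and 66%, so a loss of 24%, 35% and 34%. Intervals are 15%, 24% and 23% wider.

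**Both cuts in one three-level model (not planned).**
- A: groups 0.45, 0.37, 0.18; (1 − 0.1476)/3 = 0.2841; 87%
- B: groups 0.30, 0.48, 0.22; (1 − 0.1482)/3 = 0.2839; 88%
- C: groups 0.15, 0.55, 0.30; (1 − 0.1968)/3 = 0.2678; 85%

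The loss would be about 12-15%, with intervals 7%, 7% and 9% wider.

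**Sensitivity to the distributions.** In a second, wider set of assumed distributions, the better of the two comparisons loses between 22% (10% scoring 0-2, 40% dead) and 50% (15% scoring 0-2, 20% dead). The combined three-level loss runs from 12% to 29%.

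**Check by simulation.** Ordered logit models with 200 versus 200 patients, odds ratio 1.5 and 200 runs gave a variance ratio, ordinal to 0-2 cut, of 0.77 when 46% of the reference group scored 0-2 and 0.47 when 15% did. These are losses of about 23% and 53% for the 0-2 cut alone. The second lies a little below the formula's 60% because the comparison group's 0-2 proportion is higher, at 21%.

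**The case against.** The strongest reply is that death is not lost. A reader who stops at the 0-2 proportion might infer that all differences among scores 3 to 6 count for nothing, and that a quarter to over half of the information is discarded. The documents do not support that. Mortality at 90 days is in the same sentence of SAP section 10, so a shift from 3-5 to 6 is shown for every subgroup with an interval. The figure of over half applies to the 0-2 cut taken alone, and needs a 0-2 proportion near 20% or lower, which the documents do not state. What survives is that two separate binary displays do not make one ordinal estimate, and both are blind within 0-2 and within 3-5.

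A reader might also infer that the plan loses power. It does not, in any planned sense: no test and no sample size calculation exist.

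Third, the planned contrast is most naturally a difference in proportions, and its interval is not too wide for that quantity. The widths above are on the log-odds scale and assume a common odds ratio. This stands: the ordinal estimate answers a broader question and would be added, not substituted.

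Finally, the 0-2 cut has a plain meaning on the protocol's own scale (independence in one's own affairs), and the open-ended modelling step does not exclude an ordinal model. Both are true, but that step follows only a notable difference, and no ordinal method is named.

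**Conclusion.** The point holds as an optional improvement. SAP section 10 compares the 90-day mRS by subgroup through two separate binary outcomes, so shifts within 0-2 or within 3-5 are not seen and no estimate uses the full scale. In the three main illustrations, the better of the two planned comparisons loses about a quarter to a third of the ordinal information; the wider set of assumptions gives 22% to 50%. Combining the two cuts in one model would reduce the loss to about 12-15% in the main illustrations.

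All of these sizes rest on proportional odds and assumed mRS distributions. The blindness within 0-2 and within 3-5 rests on neither; it follows from the definitions. Because the registry is descriptive, the consequence is less precise and less complete subgroup contrasts. No planned conclusion is invalidated.

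**What to change.** In SAP section 10, add for each subgroup factor, within each stroke type:
- the distribution of the 90-day mRS over all seven levels;
- a common odds ratio with 95% CI from a proportional-odds model, or the Mann-Whitney probability with 95% CI where proportional odds is doubtful.

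Keep the 0-2 proportion and 90-day mortality as planned displays.

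The cost is a few sentences of SAP text, one more table per subgroup factor and a proportional-odds assumption to check. The full score is already collected, so no new data are needed.

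### SAP section 10 relates age and onset-to-procedure time to outcomes and clot features only through two-level splits, which costs precision and may miss gradients

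*Combined protocol and SAP*

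**What the plan says.** SAP section 10 sets out to show how baseline conditions bear on mTICI, 90-day mortality, discharge NIHSS, 90-day mRS 0 to 2 (if available) and several clot characteristics. It introduces its list with "The subgroups below will be used for these analyses". Two entries are naturally continuous variables cut once:

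- "Age (Less than 65 or 65 and older"
- "Time of stroke onset to procedure. (6 or less hours or More than 6hrs in Ischemic subgroup only"

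The planned output is: "Descriptive statistics and 95% confidence intervals will be presented for each subgroup and the difference between subgroups". SAP section 5 adds: "All confidence intervals presented will be two-sided".

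Modelling appears in three places:

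- SAP section 10, as a conditional second step: "Notable differences between subgroups will be further evaluated using additional covariates and multivariate modeling to describe relationships between subgroups and clinical outcomes".
- SAP section 8, without a condition but also without detail: "Exploratory multivariate analyses will be conducted". Protocol section 10.8 has the same general statement.
- SAP section 11, where logistic regression and random effects may be used to examine site differences. Age is among the key variables compared across sites.

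None of these says how age or time would be entered.

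**The concern.** A single cut treats patients aged 64 and 66 as different and patients aged 66 and 90 as alike. The same happens either side of 6 hours. If outcome or clot composition changes steadily with age or elapsed time, the two-group contrast uses only part of what was collected and says nothing about the shape of the relation.

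The structure of SAP section 10 makes this harder to recover later, for three reasons:

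- A model is reached only if the split already shows a notable difference, so a gradient blurred by the cut may never be modelled.
- The models are to describe relations between subgroups and outcomes, so the exposure named is still the category.
- The sentence covers clinical outcomes only. For clot size, weight, volume and histology, the two-level contrast is the only analysis of age or time that section 10 specifies.

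This bears on the registry's purpose, which is to relate clinical presentation to specimen findings. The protocol's introduction describes clot maturation as a gradual process and links good outcome to how promptly the clot is removed. One cut-point cannot display a gradual relation.

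**Working it through.** The plan gives no power, precision or information figure to reproduce. The check asks how much a two-level split keeps compared with using the variable as measured.

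**Inputs from the documents:** cut at 65 years for age; cut at 6 hours for time, ischemic patients only (SAP section 10); 95% two-sided intervals (SAP sections 5 and 10); up to 400 patients (SAP section 3).

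**Inputs assumed, because the documents do not give them:** the distribution of each variable, the share of patients on each side of the cut, and a linear relation with the outcome.

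**Step 1. Information kept.** For a normal covariate with a linear effect, cut so that a share p lies below the cut, the information kept is the squared correlation between the covariate and its indicator: φ(z_p)² / [p(1−p)], where φ is the standard normal density and z_p the p-quantile.

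- p = 0.5: 0.3989² / 0.25 = 0.637
- p = 0.3: 0.3477² / 0.21 = 0.576
- p = 0.2: 0.2800² / 0.16 = 0.490

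**Step 2. Patient equivalents for age, all 400 observed.** Multiplying the three values by 400 gives about 255, 230 and 196.

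**Step 3. Plausible range for age.** With an assumed mean of 60 to 75 years and SD of 12 to 16, the share under 65 runs from 0.66 down to 0.20, and the loss from 36% to 51%.

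**Step 4. Range for onset time.** A lognormal time was simulated (assumed median 4 to 10 hours, log-SD 0.5 to 0.9; 1,000,000 draws per setting) and cut at 6 hours. The loss is 1 minus the squared correlation between time and the indicator.

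| Assumed relation | Information lost |
|---|---|
| Linear in log-time | 36% to 57% |
| Linear in hours | 39% to 82% |
| Linear in hours, times capped at 24 h | 39% to 73% |
| Step exactly at 6 h | none |

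No patient equivalent can be given for onset time, because the number of ischemic patients is not stated.

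**Step 5. What this does to an estimate.** The ratio of estimate to standard error shrinks by the square root of the information kept: √0.637 = 0.80, √0.576 = 0.76, √0.490 = 0.70. As an illustration only, since no formal tests are planned: a correlation of 0.14 in 400 patients would have 80% power at two-sided 0.05 on the continuous scale (Fisher z). It would have about 61% after a 50/50 split and about 54% after a 25/75 split.

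**The case against.** The strongest reply is that this is a descriptive, hypothesis-generating registry with no formal testing and no sample size calculation. Two-level rows with confidence intervals are easy to read and suit that aim. Categorising in a table does not delete the underlying values, and SAP section 14 allows documented changes. All of this stands, and it limits the consequence.

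Several stronger conclusions that a reader might draw are not supported:

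- *That continuous modelling is ruled out.* The exploratory models in SAP section 8 are unconditional and their terms are unspecified. The documents are silent, not prohibitive.
- *That both variables are recorded exactly.* This is a fair inference for age. Protocol section 5.5 lists procedural time points generically, among items that may be captured. Onset time is not named as a data item and its precision is not stated, although the 6-hour split requires some onset-to-procedure time.
- *That the 400-based equivalents apply throughout.* They fit age with complete data. The time split is limited by "6 or less hours or More than 6hrs in Ischemic subgroup only", 400 is a ceiling, and 90-day mRS comes from an optional telephone visit.
- *That a loss of a third to a half is established.* It depends on an assumed distribution and a linear relation.
- *That other contrasts will be under-adjusted.* Nothing says the two-level versions will serve as adjustment covariates. Residual confounding within categories would arise only if they did.

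**Conclusion.** The point holds as a low-cost improvement. For age and onset-to-procedure time, the only association analyses that SAP section 10 specifies are two-level contrasts, and no other section supplies a continuous one.

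For age, the loss is about 36% to 51% of the information, given a roughly normal distribution, a roughly linear relation and a split no more extreme than about 20/80. For onset time the same range is reasonable if the relation is linear in log-time and the split is not extreme. The loss could be well above half if the relation is linear in skewed hours. If the true relation is a step at the cut, nothing is lost.

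The consequence is wider uncertainty in exploratory estimates and a chance of missing gradients. The documents do not support a claim that any primary result is invalid.

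**What to change.** In the SAP:

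1. Keep both two-level splits as descriptive rows.
2. In section 10, add estimates with 95% confidence intervals for the association of age (per 10 years) and onset-to-procedure time (per hour or per log-hour, in ischemic patients with a recorded time) with each listed outcome and clot characteristic. Add a 3-knot spline as a check on linearity.
3. State that these estimates are reported whether or not the split shows a notable difference.
4. State that age and onset-to-procedure time enter on the continuous scale whenever they serve as covariates in the models of sections 8, 10 and 11.

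The cost is a little extra modelling and a few more exploratory estimates to report. No additional data are requested; the time analysis uses whatever recorded times the 6-hour split already relies on.

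### SAP 10 gives intervals for differences by age, gender, race, ethnicity, smoking and COVID status in a set pooling two diseases, and attaches no stratification by or adjustment for stroke type

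*Combined protocol and SAP*

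**What the plan says.** SAP 7.1 defines one analysis set: "All enrolled subjects will be analyzed under the intent-to-treat (ITT) principle". Enrollment covers ischemic stroke patients having thrombectomy and patients having minimally invasive hematoma evacuation, up to 400 in total. No split between the two is given.

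SAP 10 states its purpose as "To evaluate the impact of baseline conditions on procedural and clinical outcomes as well as clot characteristics". The outcomes are mTICI, 90-day mortality, discharge NIHSS, mRS 0 to 2 at 90 days where available, and "clot characteristics of gross appearance, clot sign, size, weight, volume and histology". For the listed factors, "Descriptive statistics and 95% confidence intervals will be presented for each subgroup and the difference between subgroups". The set is fixed by "These analyses will be performed in the Intent-to-Treat population given adequate numbers for robust analysis".

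Stroke type is the first factor in the list, but it stands beside the others and does not stratify them. Onset-to-procedure time is the only factor restricted to one disease in words; hemorrhage location is restricted by its nature. Age, gender, race, ethnicity, smoking and COVID status carry no such restriction.

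Two further steps bear on the point. SAP 10 adds: "Notable differences between subgroups will be further evaluated using additional covariates and multivariate modeling to describe relationships between subgroups and clinical outcomes". SAP 8 adds: "Exploratory multivariate analyses will be conducted". SAP 11 also mentions stratified and modeling techniques, but for differences between centers.

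**The concern.** The two groups have different diseases, different procedures and different specimens. Protocol 5.5.3 takes thrombectomy clot from the filter. Protocol 5.5.4 takes hematoma material from the canister, possibly as fragments. If the hematoma share differs between, say, younger and older patients, and an outcome differs between the diseases, a pooled age difference mixes age with disease. It can show a difference present in neither disease, or hide one present in both.

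SAP 10 sets out to show what baseline conditions do, and SAP 2 asks about patients who look alike at presentation. An estimate that shifts with disease mix answers neither question well. At stake is the reading of published descriptive tables and the hypotheses drawn from them.

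**Working it through.** **No figure to reproduce.** The documents give no sample size calculation, disease split, share by factor or outcome gap. Every rate and share below is an assumption. Only the ceiling of 400 patients and the two-sided 95% interval come from the plan.

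**Formula.** Let m1 and m2 be the hematoma shares in the two levels of a factor, and suppose the factor has the same true effect in both diseases. Then

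pooled difference = true difference + (m1 − m2) × (hematoma rate − ischemic rate).

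The second term is zero if m1 = m2 or if the two rates are equal.

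**mRS 0 to 2, no true difference.**
- Mild case, shares 30% and 20%, rates 40% ischemic and 30% hematoma: 0.10 × (−0.10) = −1.0 point.
- Larger case, shares 40% and 15%, rates 45% and 25%: 0.60×0.45 + 0.40×0.25 = 37.0% against 0.85×0.45 + 0.15×0.25 = 42.0%, so −5.0 points.

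The pooled half-width is 1.96 × √(p1q1/n1 + p2q2/n2). In the larger case this is 9.57 points at 200 v 200 and 15.81 at 40 v 360.

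| Chance that the pooled interval excludes zero, no true difference | 200 v 200 | 40 v 360 |
|---|---|---|
| Mild case | 5.5% | 5.2% |
| Larger case | 17.6% | 9.5% |

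The 90-day visit is optional. If 60% attend, the larger case gives 12.5% at 120 v 120 and 7.7% at 24 v 216.

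**mRS 0 to 2, masking.**
- Larger case, true +5 points in both diseases: 0.60×0.50 + 0.40×0.30 = 42.0% against 42.0%. The pooled difference is 0.0.
- Larger case, true +10: pooled +5.0. The interval excludes zero 17.2% of the time pooled against 50.7% stratified (200 v 200), and 9.2% against 22.7% (40 v 360).
- Mild case, true +10: pooled +9.0. The figures are 44.8% against 52.8%, and 19.2% against 22.7%.

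**Continuous clot measure, no true effect.** With the diseases D standard deviations apart, the distortion is (m1 − m2) × D and the variance per level is (1 + m(1 − m)D²)/n.

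| Shares | D | Distortion (SD) | Excludes zero, 200 v 200 | 40 v 360 |
|---|---|---|---|---|
| 30% and 20% | 0.5 | 0.05 | 7.8% | 6.0% |
| 30% and 20% | 1 | 0.10 | 15.1% | 8.5% |
| 40% and 15% | 0.5 | 0.125 | 23.1% | 11.3% |
| 40% and 15% | 1 | 0.25 | 63.2% | 27.2% |

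**Price of stratifying.** Use Mantel-Haenszel weights w = ab/(a + b), where a and b are the numbers in the two levels within a disease. In the larger case at 200 v 200 the strata are 120 v 170 and 80 v 30, so w = 70.34 and 21.82. With no true effect the half-width is 1.96 × √(70.34×0.2475 + 21.82×0.1875) / 92.16 = 9.86 points, against 9.57 pooled. At 40 v 360 it is 15.84 against 15.81.

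**What the existing steps catch.** A large spurious difference in a clinical outcome may be judged notable and modeled, and stroke type may then be chosen as a covariate. A masked difference is small by construction and need not trigger the modeling. The modeling sentence does not reach clot characteristics. SAP 8's analyses name no factor, outcome or covariate.

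**The case against.** The strongest case is that SAP 10 names no estimator. A reader might infer that it prescribes crude differences. It does not say so: naming the ITT set fixes who is included, not how tables are laid out, and within-disease tables would also comply. This stands. The defect is that no stratification or adjustment is attached to the reported difference, not that one is ruled out.

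A reader might also infer that the plan ignores disease altogether. It does not. Stroke type has its own comparison, notable differences go to modeling, and exploratory multivariate analyses are planned unconditionally. These steps reduce the problem but leave the gaps shown above.

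A third argument is that a marginal difference across everyone enrolled is a legitimate description, since age, gender, race and ethnicity are not caused by stroke type. That is fair for a registry without formal testing, and it is a reason to keep the pooled figure. It is weaker as a reason to show only that figure, given SAP 10's stated aim of evaluating impact.

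Scope has limits too. mTICI is collected in ischemic patients only (Protocol 5.5), so it is unaffected. Clot sign may be unaffected as well: the only one the documents describe is the hyperdense sign in thrombectomy patients (Protocol 1.1).

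Finally, every magnitude is assumed and the mild mRS case is almost nominal. Whether an interval excludes zero is only a yardstick here, because the plan bases no decision on it.

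**Conclusion.** The point holds as a minor one. Applied as written, SAP 10 lets disease mix enter the differences for six factors, and its conditional modeling cannot be relied on to remove it, least of all for masked differences and clot characteristics.

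The gap in the wording is certain; the size of any distortion is not. It is zero with equal mix or equal outcomes by disease. For mRS 0 to 2 it is 1 point in the mild case and 5 points in the larger one. For a continuous clot measure it is 0.05 to 0.25 SD over the assumed range. The larger figures need a 25-point imbalance in hematoma share together with a 20-point outcome gap or a gap of 0.5 to 1 SD. No document supports or excludes these values.

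A reader might infer that the subgroup tables will be materially wrong. The documents do not support that, since they give neither shares nor outcome gaps. The Protocol Synopsis makes all analyses descriptive and hypothesis generating, so no decision rule is affected.

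**What to change.** In SAP 10, for age, gender, race, ethnicity, smoking and COVID status:

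- For every outcome measured in both diseases, report the difference stratified by stroke type beside any pooled difference. Mantel-Haenszel weights would serve for proportions, and stroke type as a covariate for continuous measures.
- Name stroke type as a covariate in the follow-up models.
- Do not pool clot size, weight, volume or histology across the two specimen types without that adjustment.

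Full within-disease tables are optional where numbers allow; requiring them would go further than the gap demands. In the larger case the half-width for mRS 0 to 2 within hematoma patients is 1.96 × √(0.25×0.75×(1/80 + 1/30)) = 18.2 points at 200 v 200. With 16 v 54 patients (40 v 360 overall) it is 24.2.

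The cost is a few sentences, some extra table columns and slightly wider intervals. Stroke type is already recorded. Sparse race or COVID cells remain subject to SAP 10's existing condition on sufficient numbers.
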